#### Which Committee will review this protocol?

- The Clinical Research Committee - (CRC)

## **1.0 OBJECTIVES**

### **1.1 Primary Objectives**

#### **Phase I**

1. To determine the maximum tolerated dose (MTD) and the recommended phase 2 dose (RP2D) and dose limiting toxicity (DLT) of the combination of selinexor with sorafenib in FLT3-ITD and –D835 mutated patients with relapsed/refractory acute myeloid leukemia (AML).

#### **Phase II**

1. To determine the composite CR (CRc) rate including CR (complete remission) + CRp (complete remission with incomplete platelet recovery) + CRi (complete remission with incomplete count recovery) within 3 months of treatment initiation in FLT3-ITD and –D835 mutated patients with relapsed/refractory AML.

### **1.2 Secondary Objectives**

#### **Phase I**

1. To determine the composite CRc rate including CR + CRp + CRi within 3 months of treatment initiation in FLT3-ITD and –D835 mutated patients with relapsed/ refractory AML.
2. To determine the partial response (PR), marrow clearance rate, bone marrow blast reduction  $\geq 50\%$  within 3 months of treatment initiation in FLT3-ITD and –D835 mutated patients with relapsed/ refractory AML.
3. To determine the duration of response (DOR), event-free survival (EFS), overall survival (OS), and number of patients bridged to hematopoietic stem cell transplant (HSCT) and median duration to HSCT from the initiation of the combination of selinexor with sorafenib in FLT3-ITD and –D835 mutated patients with relapsed/ refractory AML.
4. To determine the safety of the combination of selinexor with sorafenib in FLT3-ITD and –D835 mutated patients with relapsed/ refractory AML.

#### **Phase II**

1. To determine the PR, marrow clearance rate, bone marrow blast reduction  $\geq 50\%$  within 3 months of treatment initiation in FLT3-ITD and –D835 mutated patients with relapsed/ refractory AML.
2. To determine the DOR, EFS, OS, and number of patients bridged to HSCT and median duration to HSCT from the initiation of the combination of selinexor with sorafenib in FLT3-ITD and –D835 mutated patients with relapsed/ refractory AML.
3. To determine the safety of the combination of selinexor with sorafenib in FLT3-ITD and –D835 mutated patients with relapsed/ refractory AML.

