such patients achieve marrow responses to *FLT3* inhibitors, with 20-30% bridged to allogeneic stem cell transplant. Responses to *FLT3* inhibitors last 3-6 months and are invariably transient (except among patients who undergo transplantation) due to the emergence of resistance. The primary cause of resistance is the acquisition of point mutations in the *FLT3* kinase domain (KD). Heidel et al first to identified point mutations in the *FLT3-ITD* KD as a mediator of resistance to the *FLT3* inhibitor midostaurin. They reported a single amino acid substitution at position 676 (N676K) within the *FLT3* KD as the sole cause of resistance to midostaurin in a patient with AML. Acquired point mutations in the KD may be preexisting or acquired after exposure to the *FLT3* inhibitors as has been shown with midostaurin. Homology modeling has identified two main types of *FLT3* mutations, namely TKD1 mutations involving the ATP-binding (hinge regions) and the TKD2 mutations involving the activation loop. Non-mutational mechanisms of resistance include up-regulation of compensatory pathways including the MAPK/ERK, *PI3K/Akt/mTOR*, *FOXO3A*, *SYK*, and *STAT5/PIM* pathways, up-regulation of the *FLT3* ligand or receptor, mutations in other kinases (e.g. *CBL*), activation of anti-apoptotic proteins *BCL2*, *MCL1* and *BCL-x(L)*, and tumor microenvironment mediated resistance.

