### 3.5 Phase II expansion

Once MTD is defined, the RP2D will be selected based on efficacy and safety result from the phase I in discussion with the PI, the sponsor and the supporting company (Karyopharm). The Investigator is responsible for completing the cohort summary template prior to advancing subjects to the phase II portion. The phase II portion will start in two cohorts as defined previously with 20 patients per cohort. Any patients still on study from the phase I portion at a dose lower than RP2D can be dose escalated up to RP2D in accordance with the dose escalation guidelines in section 5.2.3.

However, the dose for any patient may never exceed the RP2D.

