## 11.0 STATISTICAL CONSIDERATIONS

The primary objectives of the study are to evaluate safety and efficacy of selinexor in combination with sorafenib in patients with FLT3-ITD and -D835 mutated AML. The total accrual is 52 patients (Phase I: up to 12 patients and Phase II: 20 patients per cohort).

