### 11.3 Statistical Analysis Plan

All patients who received any dose of the study agent will be included in the analysis for efficacy and safety. Demographic/clinical characteristics (including duration of response) and safety data of the patients will be summarized using descriptive statistics such as mean, standard deviation, median and range. For the primary efficacy analysis, we will estimate the ORR for the combination treatment, along with the 95% confidence interval. In addition, we will estimate composite CRc rate, partial response and marrow clearance rate within 3 months by FLT3 mutation. Patients who drop out of the study before completing all the cycles will be treated as “failures” for the primary analysis. ORR during the study period will also be presented with the 95% confidence interval. The association between ORR and patient’s clinical characteristics will be examined by Wilcoxon’s rank sum test or Fisher’s exact test, as appropriate. Toxicity type, severity and attribution will be summarized for each patient using frequency tables.

The distribution of time-to-event endpoints (DFS and OS) including overall survival and progression free survival will be estimated using the method of Kaplan and Meier. Comparisons of time-to-event endpoints by important subgroups will be made using the log-rank tests. Paired t-tests will be used to determine the immunological and molecular changes in the peripheral blood and bone marrow from baseline to the time of response, and to the time of disease progression.

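### Time to HSCT has no stated population or rule for death before transplant, and duration of response is not separated at HSCT, so a reported duration would mix regimen and transplant effects

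*Combined protocol and SAP*

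**What the plan says.** Section 1.2 sets, for phase II, the "number of patients bridged to HSCT and median duration to HSCT from the initiation of the combination of selinexor with sorafenib" as a secondary objective beside DOR, EFS and OS. The phase I list has the same objective. No population is attached to the median.

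Section 2.1 (repeated in 2.3) reports, for FLT3 inhibitors in relapsed/refractory FLT3-ITD AML, marrow responses in 40-50%, "with 20-30% bridged to allogeneic stem cell transplant", and responses lasting 3-6 months that are "invariably transient (except among patients who undergo transplantation) due to the emergence of resistance". Section 2.3 hopes that adding selinexor will lengthen response to sorafenib.

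Section 8 defines response categories and relapse. It does not define DOR and gives no rule for transplant. Section 11.3 lists DOR with the characteristics to be summarised by mean, standard deviation, median and range. Its time-to-event sentence names DFS, OS and progression-free survival, which "will be estimated using the method of Kaplan and Meier". HSCT does not appear in 11.3, and neither does EFS.

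On size, section 3.5 states: "The phase II portion will start in two cohorts as defined previously with 20 patients per cohort".

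**The concern.** A median time to an event that most patients never have depends on who is counted. Over all treated patients, the median exists only if at least half are transplanted. Among transplanted patients only, it leaves out everyone who died first, so faster death can make it look shorter. The plan does not choose between these readings, and the choice could be made after the data are seen.

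DOR has a related gap. The protocol itself says that transplant changes how long a response lasts, and it hopes the combination will do the same. There is no control arm, and the target CRc rates imply only about 7 responders (35% of 20, FLT3-inhibitor-naive cohort) and 4 responders (20% of 20, FLT3-inhibitor-failure cohort). With so few, an unstated transplant rule could largely decide the reported DOR. Mean and SD also have no defined meaning for responses still ongoing at last contact.

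**Working it through.** **The plan's own figures.** No precision or sample size is given for HSCT or DOR, so there is none to reproduce on this point. Accrual adds up: 12 + 20 + 20 = 52. The early-stopping probabilities at toxicity 0.30 reproduce exactly from the printed boundaries: 0.2384 in Table 8 (response 0.35) and 0.2820 in Table 11 (response 0.20). They use only response and toxicity counts, so nothing below affects them.

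**Median over all treated patients.** Inputs: n = 20 per cohort (3.5) and a 20-30% bridging rate p (2.1, background). With death as a competing event, the median exists only if X ≥ 10, where X ~ Binomial(20, p).

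| p | Expected bridged | P(X ≥ 10) |
|---|---|---|
| 20% | 4 | 0.3% |
| 25% | 5 | 1.4% |
| 30% | 6 | 4.8% |
| 40% | 8 | 24.5% |
| 50% | 10 | 58.8% |

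The last two rows show the dependence on p. They are not document figures.

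**Median among transplanted patients.** At least one transplant occurs with probability 1 − (1 − p)^20, which is 98.9% at p = 20% and 99.9% at p = 30%. So a median can nearly always be calculated, but from about 4-6 values. The interval from smallest to largest value covers the true median with probability 1 − 2(0.5)^m: 87.5% for m = 4, 93.75% for m = 5 and 96.9% for m = 6.

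Its direction can mislead. Assume constant monthly hazards of 0.05 for HSCT and 0.15 for death without HSCT. The share ever transplanted is 0.05/0.20 = 25%, and the median among them is ln 2/0.20 = 3.5 months. Doubling the death hazard to 0.30 gives 0.05/0.35 = 14% transplanted and a median of ln 2/0.35 = 2.0 months. Time to HSCT looks faster while fewer patients get there.

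**Number bridged.** Exact 95% CI: 4/20 = 20% (5.7-43.7%); 6/20 = 30% (11.9-54.3%). The count is interpretable on its own.

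**DOR.** From the background rates, the share of responders transplanted runs from 20/50 = 40% to 30/40 = 75%, if only responders are bridged.

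Assume a 4.5-month median without HSCT (midpoint of 3-6), transplant at 2 months among those still in response, and a relapse hazard halved afterwards.
- Hazard h = ln 2/4.5 = 0.154 per month. Still in response at 2 months: s = exp(−2h) = 73.5%.
- For t > 2, with a share q of all responders transplanted: S(t) = (s − q)·exp(−h(t − 2)) + q·exp(−(h/2)(t − 2)). Set S(t) = 0.5.
- q = 40%: 5.5 months. q = 50%: 5.9 months. q = s, everyone still in response: 7.0 months, the maximum.

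None of these includes any selinexor effect. Because s = 73.5%, the 75% share cannot occur under these inputs.

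Range over the starting median, from q = 40% to q = s: 3.5-4.0 months if it is 3 months, and 7.5-10.0 if it is 6. If transplant leaves the hazard unchanged, DOR stays at its starting value.

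**The case against.** The objective pairs a count with a median, and the natural reading is the median among those bridged. That median can be calculated. This stands: a reader might infer that the objective cannot be estimated at all, but that is true only of the all-treated reading. The 20-30% is also history for FLT3-ITD patients on FLT3 inhibitors, not a planning value.

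A reader might also infer that the plan would run Kaplan-Meier on time to HSCT with deaths censored and so overstate transplant. Section 11.3 does not plan this: its Kaplan-Meier sentence names DFS, OS and progression-free survival only.

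Nor do the documents support saying that these summaries show nothing about the combination, or that they would rank a worse regimen higher. The number bridged is reported beside the median. In the hazard example it falls from 25% to 14% and exposes the worse regimen.

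It is tempting to claim a larger transplant effect on DOR. The mixture (1 − p)·exp(−ht) + p·exp(−(h/2)(t − 2)) gives 6.6 months at p = 40% and 9.0 at p = 75%. But it keeps every future transplant recipient relapse-free to month 2, which is immortal-time bias. Drawing recipients from those still in response gives the 5.5 and at most 7.0 months above. At a 4.5-month starting median with 40-50% transplanted, DOR stays within the cited 3-6 months.

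The background rates also do not carry over cleanly to the CRc targets. Four to six bridged out of 7 responders would be 57-86%, and the failure cohort's target gives only 4 responders.

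Finally, these are descriptive secondary objectives, and following patients through HSCT is a legitimate choice. Both points are fair, but neither supplies the missing definitions.

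**Conclusion.** The point holds as a gap in definition and analysis, not as a failure of the trial. The time-to-HSCT objective names no population and no treatment of death before HSCT. At 20-30% bridged, the all-treated median would be reached in 0.3-4.8% of cohorts of 20. The transplanted-only median rests on about 4-6 selected values and should be read only beside the number bridged.

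DOR as planned has no definition, no handling of censored values and no separation at HSCT, so it would mix regimen and transplant effects. The illustrated shift, from 4.5 months to 5.5 and at most 7.0, depends on the assumed transplant time, halved hazard and starting median. The mixing itself follows from the protocol's statement that transplant is the exception to transient response.

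CRc within three cycles and the stopping rules do not depend on any of this. The change is worth making before results are seen.

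**What to change.** In section 11.3, for each phase II cohort:

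- Report the number bridged to HSCT with an exact 95% CI.
- Report the cumulative incidence of HSCT at 3 and 6 months from treatment start, with death without HSCT as a competing event.
- Give the median time to HSCT among transplanted patients only, labelled as a description conditional on transplant.
- Define DOR and EFS (start, events, censoring). Estimate both by Kaplan-Meier following through HSCT, and again censored at the HSCT date as a sensitivity analysis. Drop the mean and SD for DOR.
- Leave OS uncensored at HSCT.

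The cost is SAP wording and a few extra estimates. The HSCT date is already needed for the objective. The HSCT-censored estimates will be less precise, and the censoring is informative because transplant selects patients in response. They should therefore stand beside the through-HSCT estimates and not replace them.

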### **1.3 Exploratory Objectives**

1. To evaluate the response rate, EFS and OS in FLT3 mutated/NPM1 wild-type patients versus FLT3 mutated/NPM1 mutated versus FLT3 wild-type/NPM1 mutated patients treated with the combination of selinexor and sorafenib.
2. Quantitative changes of FLT3-ITD and –D835 allelic burden with time in patients treated with the combination of selinexor and sorafenib.
3. To evaluate the extent of pharmacodynamics biomarker (such as p-FLT3, p-p70S6K, pERK) inhibition and the induction of apoptosis in the bone marrow and peripheral blasts following treatment with the combination of selinexor and sorafenib.
4. To investigate possible relationships between selinexor and other baseline gene expression signatures and clinical response.
5. To store and/or analyze surplus blood or tissue including bone marrow, if available, for potential future exploratory research into factors that may influence development of AML and/or response to selinexor (where response is defined broadly to include efficacy, tolerability or safety).
6. To evaluate the pharmacodynamic effects of treatment on induction/inhibition of XPO1 using qRT-PCR and on plasma protein/cytokine levels.

## 2. BACKGROUND

### 2.1 FLT3-mutated AML

*FLT3* (FMS-like tyrosine kinase III) belongs to the Class III family of receptor tyrosine kinases (RTKs; other members of this family include receptors for KIT, FMS, and PDGF) . Signaling via RTKs is frequently deregulated in hematological malignancies . *FLT3* is expressed on the leukemic cells of 70–100% of patients with AML . Additionally, activating mutations in *FLT3* are observed in 30% of adult AML patients . The two *FLT3* mutations found in AML include internal tandem duplications in the juxta-membrane domain (ITD, 17–34%) and mutations in the tyrosine kinase domain (TKD) activation loop (7%) . *FLT3* stimulates survival and proliferation of leukemic blasts . *FLT3*-ITD mutations are associated with adverse prognosis. Patients with *FLT3*-ITD have significantly elevated peripheral blood white cell counts, increased bone marrow blasts, increased relapse risk, inferior event-free survival (EFS), and decreased overall survival (OS) . The *FLT3*-TKD mutations have unknown prognostic significance in AML .

Several small-molecule *FLT3* targeted tyrosine kinase inhibitors (TKIs) that are undergoing evaluation in phase I, II, and III trials have shown promising activity as single agents and in combination with hypomethylating agents or chemotherapy. These include quizartinib (AC220), sorafenib, midostaurin (PKC412), lestaurtinib, and crenolanib. These TKIs act as direct inhibitors of *FLT3* via competitive inhibition of ATP-binding sites in the *FLT3* receptor KD.

*FLT3* inhibitors demonstrate potent anti-leukemic activity and improve outcomes in patients with relapsed/refractory AML and *FLT3*-ITD mutations. About 40-50% of

such patients achieve marrow responses to *FLT3* inhibitors, with 20-30% bridged to allogeneic stem cell transplant. Responses to *FLT3* inhibitors last 3-6 months and are invariably transient (except among patients who undergo transplantation) due to the emergence of resistance. The primary cause of resistance is the acquisition of point mutations in the *FLT3* kinase domain (KD). Heidel et al first to identified point mutations in the *FLT3-ITD* KD as a mediator of resistance to the *FLT3* inhibitor midostaurin. They reported a single amino acid substitution at position 676 (N676K) within the *FLT3* KD as the sole cause of resistance to midostaurin in a patient with AML. Acquired point mutations in the KD may be preexisting or acquired after exposure to the *FLT3* inhibitors as has been shown with midostaurin. Homology modeling has identified two main types of *FLT3* mutations, namely TKD1 mutations involving the ATP-binding (hinge regions) and the TKD2 mutations involving the activation loop. Non-mutational mechanisms of resistance include up-regulation of compensatory pathways including the MAPK/ERK, *PI3K/Akt/mTOR*, *FOXO3A*, *SYK*, and *STAT5/PIM* pathways, up-regulation of the *FLT3* ligand or receptor, mutations in other kinases (e.g. *CBL*), activation of anti-apoptotic proteins *BCL2*, *MCL1* and *BCL-x(L)*, and tumor microenvironment mediated resistance.

Sorafenib is an orally active multikinase inhibitor with potent activity against *FLT3* and the Raf/ERK/mitogen-activated protein kinase pathway. Sorafenib is 1000-fold more active against ITD mutant *FLT3* than wild-type *FLT3* in cell based assays. In phase I studies, sorafenib potently inhibited *FLT3-ITD* leukemic blasts. Melzelder et al reported clinical activity as a single agent in relapsed *FLT3-ITD* AML. We performed a phase I/II study of idarubicin, high-dose cytarabine and sorafenib in AML patients (median age = 53 years). In this study 15 *FLT3-ITD* patients were enrolled. Fourteen patients achieved a CR and 1 patient achieved complete remission with incomplete platelet recovery (CRp). Mutant *FLT3* was suppressed in all 10 patients evaluated, with fivefold greater suppression of mutant *FLT3* as compared to wild-type *FLT3* on plasma inhibitory assays. We recently reported the feasibility and efficacy of combining hypomethylator therapy (5-azacytidine) with sorafenib in patients with relapsed/refractory *FLT3-ITD* AML. A total of 43 patients were treated (93% were *FLT3-ITD* mutated). Patients had received a median of 2 prior therapies. The response rate was 46% including CR, CRp and CRi (complete remission with incomplete recovery of counts). This response rate compares favorably with expected response rates in multiply relapsed AML. 64% of the patients achieved >85% *FLT3* inhibition during their first cycle of therapy. The combination was reasonably well tolerated. Although hepatotoxicity was seen, most instances were grade 1 or 2.

Over 10 major tumor suppressor pathways have evolved in order to prevent the development and progression of neoplasia. The majority of the tumor suppressor (TSP) and growth regulatory (GRP) proteins mediating these pathways act in the cell nucleus downstream of signaling pathways. Accumulating data suggest that in order to maintain their malignant behavior, neoplastic cells must inactivate most or all of the known TSP and GRP pathways. Active nuclear export of TSP/GRP is one very efficient and rapid means of overcoming the normal cell cycle and genomic instability checkpoints mediated by these proteins. Essentially all known TSP/GRP utilize a

single nonredundant nuclear export protein complex in order to exit the nucleus. Exportin 1 (XPO1), also called chromosomal region maintenance protein 1 (CRM1), is the primary component of this export complex, and is overexpressed in many types of cancer.

**Table 1: CRM1 Inhibition Enhances Multiple TSPs/GRPs**

Oncogenic Pathway	TSP/GRP Enhanced by CRM1 inhibition	Oncogenic Pathway	TSP/GRP Enhanced by CRM1 inhibition
AKT↑, PI3K↑, PTEN↓ deletion p53, MDM2↑ HER2, EGF-R p16 INK4A ↓ or p14 ARF ↓ mTOR↑ Wnt / β-Catenin ↑ deletion pRb	FOXO, p27 p21 CIP1 , p53, p14 ARF FOXO, pRB pRB, p53 p53, p27, FOXO APC, HMGBP1 p27	CDK2-CyclinE-E2F1 NPM1 Mutation c-Myc ↑ Bcr-Abl Bcl2 ↑, Bcl-xL ↑ Notch ↑ NF-κB ↑	pRb, p27, p21 CIP1 p53, p14 ARF PP2A, p21 CIP1 PP2A, Abl p53, p16 INK4A FOXO I-κB

Selinexor is a Selective Inhibitor of Nuclear Export / SINETM compound that slowly reversibly binds and inactivates XPO1, thereby forcing the nuclear retention of key TSP/GRP. Transient retention of TSP/GRP in the nucleus at high levels via XPO1 blockade activates their cell cycle checkpoint and genome surveying actions. This leads to the death of nearly all types of malignant cells, whereas normal cells undergo transient cell cycle arrest and recovery when the export block is released. Garzon et al identified a strong down-regulation of total FLT3 protein expression in primary AML samples after XPO-1 inhibition. This inhibition seems to occur at the post-transcriptional level. Based on these findings, we propose Phase I combination trial of FLT3-ITD inhibitor sorafenib (Nexavar) and SINETM compound (selinexor) in relapsed/refractory AML patients.

## 2.2 Selinexor, a Selective Inhibitor of Nuclear Export / SINETM Compound

Selinexor is an oral, first in class, slowly reversible, potent and Selective Inhibitor of Nuclear Export / SINETM compound that specifically blocks exportin 1 (XPO1). To date, other than XPO1, no targets of selinexor have been identified. Selinexor restores many of the tumor suppressor (TSP) and growth regulatory (GRP) proteins to the nucleus where they can carry out their normal functions. Selinexor is selectively cytotoxic for cells with genomic damage, i.e., for tumor cells, both *in vitro* and *in vivo*. The nuclear export of eIF4E, a protein that binds to the mRNAs of many oncogenic and growth-promoting mediators, requires XPO1 for transport to cytoplasmic ribosomes. Selinexor blocks the XPO1-mediated nuclear export of eIF4E, preventing translation of the eIF4E-bound mRNAs on ribosomes, with a reduction in levels of the cognate oncogenic and growth-promoting proteins. All cell types exposed to a SINETM compound *in vitro* undergo G1/S ± G2/M cell cycle arrest, followed by a ‘genomic fidelity’ review, and cells with damaged genomes are induced to undergo

apoptosis. Normal cells, with an intact genome, remain in transient, reversible cell cycle arrest until the export block is relieved. Selinexor and other SINETM compounds are not intrinsically cytotoxic; rather, they can restore the highly effective tumor suppressing pathways that lead to selective elimination of genomically damaged (i.e., neoplastic) cells. Tumors of hematopoietic lineage are particularly susceptible to induction of apoptosis by XPO1 inhibition; normal hematopoietic cells and their functions are largely spared.

